10.3.1. Safety Analyses

10.3.1.1. Clinical Evaluation of Safety

All IMP and protocol procedure AEs will be listed, and if the frequency of events allows, safety data will be summarised using descriptive methodology.

The incidence of symptoms for each treatment will be presented by severity and by association with IMP as perceived by the investigator. Symptoms reported to occur prior to randomisation will be distinguished from those reported as new or increased in severity during the study. Each symptom will be classified by the most suitable term from the medical regulatory dictionary.

The number of IMP-related SAEs will be reported.

10.3.1.2. Statistical Evaluation of Safety

Safety parameters that will be assessed include AEs, MRI, safety laboratory parameters, vital signs, and ECG parameters. The parameters will be listed and summarised using standard descriptive statistics. Additional analysis will be performed if warranted upon review of the data. Outliers will also be identified and listed where appropriate. Additional analyses may be performed if warranted upon review of the data. All planned safety analyses will be detailed in the SAP.

Shift tables will be constructed for each dose group to assess the incidence of and changes in vasogenic oedema and microhaemorrhage counts pre- and post-dose (by time) based on MRI.

Suicide-related thoughts and behaviours based on the C-SSRS will be listed by patient. Only time points and patients that show suicidal ideation/behaviour will be displayed (i.e., not all of the “no” responses will be displayed).

An assessment of potential QTc prolongation will be carried out in 2 ways:

1. A summary of the number of patients experiencing a maximum increase from baseline in QTcF interval will be summarised for each treatment according to the following categories: >30 ms and >60 ms. In addition, there will be a summary by treatment of the number of patients with QTcF postdose values in the following categories: >450 ms, >480 ms and >500 ms.
2. Scatter plots will be created of QTcF versus LY3303560 concentration and change from baseline QTcF versus LY3303560 concentration (for time points where there is matched LY3303560 concentration and QTcF available). Placebo data will be included in the plot with concentration imputed to zero. The reference line of 450, 480, and 500 ms will be used for the QTcF versus concentration plot; the reference line will be 10, 30 and 60 ms for the QTcF change from baseline versus concentration plot. Analysis will be performed

to assess the mean change in QTcF as a function of plasma drug concentration. The average of the triplicate QTcF measurements will be computed at each of the scheduled time points, and baseline will be the mean of the triplicate measurements collected prior to dosing at time 0 in each treatment period.

10.3.2. Pharmacokinetic Analyses

10.3.2.1. Pharmacokinetic Parameter Estimation

Standard non-compartmental methods of analysis and model-based approaches using non-linear mixed effects modeling (NONMEM) or other appropriate software may be implemented to estimate PK parameters including C_{max} , area under the concentration curve during the dosing interval (AUC τ), half-life, clearance, and volume of distribution after IV administration of LY3303560. The accumulation ratio, expressed as either AUC τ , C_{max} , or minimum observed drug concentration (C_{min}), may be reported.

An analysis of the effect of dose, concentration or demographic factors on the PK parameters may be conducted.

An analysis relating LY3303560 serum exposure to LY3303560 CSF concentrations may be conducted.

Exploratory PK analysis comparing Japanese and non-Japanese subjects may be conducted.

10.3.3. Imaging Analyses

Summary statistics of the flortaucipir F 18 standardised uptake value ratio (SUVr) will be provided by treatment (70 and 210 mg, and placebo) and visit (baseline and Visit 13 or Visit 20). Summary statistics of change from baseline and percentage change from baseline in SUVr will also be provided. Summary statistics may also be provided for SUVrs in individual and other composite brain regions if needed.

Changes in regional brain volume and functional connectivity in brain networks captured by MRI over the course of the study will be explored and summarised. Magnetic resonance imaging will be obtained every 8-12 weeks; therefore, a mixed model repeated measures (MMRM) may be conducted fitting baseline, treatment and study visit as fixed effects.

Additionally, the relationship between LY3303560 serum exposure and imaging endpoints may be explored graphically or by a modeling approach.

10.3.4. Exploratory Pharmacodynamic Analyses

10.3.4.1. Pharmacodynamic Parameter Estimation

The concentration of plasma tau, and the concentration of CSF biomarkers, including tau, p-tau, A β 1-42 and neurogranin, will be determined. Plasma and CSF biomarker data will be summarised statistically and/or illustrated graphically by time and dose. The mean change in concentration of the plasma and CSF biomarkers from predose will be evaluated.

No formal statistical analyses of biomarkers are planned.

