| 
Exploratory Objectives
 
 • To evaluate the effects of multiple doses of LY3303560 on cognitive function in patients with MCI due to AD or mild to moderate AD • To evaluate the effects of multiple doses of LY3303560 on brain atrophy in patients with MCI due to AD or mild to moderate AD • To evaluate the effects of multiple doses of LY3303560 on brain functional connectivity in patients with MCI due to AD or mild to moderate AD • To evaluate the immunogenicity of multiple doses of LY3303560 in patients with MCI due to AD or mild to moderate AD • To evaluate the effects of multiple doses of LY3303560 on plasma and CSF biomarkers in patients with MCI due to AD or mild to moderate AD • To evaluate the effects of multiple doses of LY3303560 on tau pathology using the tau tracer flortaucipir F 18 in patients with MCI due to AD or mild to moderate AD • To determine the CSF concentration of LY3303560 following multiple IV doses in patients with MCI due to AD or mild to moderate AD | 
ADAS-Cog₁₄, ADCS-MCI-ADL24, NTB, MMSE, dCDT
 
Quantitative measures of brain atrophy derived from volumetric MRI scans
 
Quantitative measures of brain functional connectivity derived from functional MRI scans
 
Detection of anti-drug antibodies (ADA)
 
Plasma tau concentration; CSF concentration of tau, p-tau, $\text{A}\beta$1-42, and neurogranin
 
Quantitative endpoints from flortaucipir F 18 PET scans
 
Mean LY3303560 concentrations in CSF
 |

| | |
|--|--|
| Exploratory Objectives (continued) | |
| 
• To explore the safety and tolerability of LY3303560 in Japanese subjects in relation to non-Japanese subjects• To explore the PK of LY3303560 in Japanese subjects in relation to non-Japanese subjects | 
Safety and tolerability will be assessed by monitoring TEAEs
 
C_{max} and $AUC\tau$
 |

[figure not shown]
5. Study Design

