5.1.3. Treatment Phase

Each cohort will consist of 8 patients randomised (6 LY3303560: 2 placebo) to a 25-week MAD treatment period (7 doses), after which they will be given the option of continuing the treatment up to 49 weeks (up to 6 further doses, Visits 14 to 19). Patients who have completed at least the 25-week treatment period will be followed up for 16 weeks after completion of dosing (Visits 20 to 24) as per the Schedule of Activities in Section 2.

Safety and PK will be assessed throughout the study for each cohort.

Safety will be monitored by AEs, ECGs, vital signs (blood pressure and pulse rate), MRIs, neurological examinations, Columbia Suicide Severity Rating Scale (C-SSRS), and safety laboratory tests. In addition, blood samples for the assessment of immunogenicity will be taken at regular intervals throughout the dosing and follow-up periods. Each patient will have 1 screening (baseline) MRI prior to dosing with LY3303560, another after approximately 4 weeks, and then at approximately 12-week intervals thereafter as specified in the Schedule of Activities (Section 2), for the assessment of any potential imaging abnormalities. Tau imaging using flortaucipir F 18, cognitive and functional assessments (Neuropsychological Test Battery [NTB], the 14-item Alzheimer's Disease Assessment Scale – Cognition [ADAS-Cog₁₄], Mini-Mental State Examination [MMSE], digital clock drawing test [dCDT], and 24-question Alzheimer's Disease Cooperative Study/Activities of Daily Living scale adapted for MCI patients [ADCS-MCI-ADL24]), and cerebrospinal fluid (CSF) (via single lumbar puncture) will be assessed/obtained as detailed in the Schedule of Activities in Section 2. If scheduled on the same day, the cognitive/functional testing should be conducted before the lumbar puncture (LP), and the LP should occur no closer than 24 hours before dosing. The patient must be free from any

post-LP headache for at least 12 hours before dosing. If the LP is performed on a separate day before the cognitive testing, the cognitive/functional testing should be performed at least 24 hours after the LP, and the patient must be free from any post-LP headache for at least 12 hours before dosing (see Section 9.5.1 for detail on CSF sampling).

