10.1. Sample Size Determination

A total of 24 patients may be enrolled to ensure 16 complete the study. The sample size is customary for Phase 1 studies evaluating safety, PK and/or PD parameters.

It is expected that at least 4 Japanese patients will be enrolled into the study. Patients will be stratified by Japanese/non-Japanese but not by disease severity at randomisation.

Patients who are randomised but do not complete the study may be replaced to ensure that enough patients complete the study (see Section 5.2).

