10.3. Statistical Analyses

Statistical analysis of this study will be the responsibility of Eli Lilly and Company or its designee.

Pharmacokinetic analyses will be conducted on the full analysis set. This set includes all data from all randomised patients receiving at least 1 dose of the IMP according to the treatment the patients actually received. Safety analyses will be conducted for all enrolled patients, whether or not they completed all protocol requirements. Pharmacodynamic analyses will be conducted on all randomised participants who take at least 1 dose of study treatment and have at least 1 postdose PD measurement relevant to the endpoint.

Summary statistics, data tabulations, and data graphs by population (Japanese and non-Japanese, and combined) will be provided as appropriate.

Analyses will be reported by dose. Patients receiving placebo will be pooled into 1 group.

All total and subscale scores will be derived from individual items. If any individual item is missing, the corresponding total and subscale scores will be considered missing, except for the

ADAS-Cog₁₄, which will be imputed. The imputation algorithm will be specified in the statistical analysis plan (SAP).

No formal hypothesis tests are planned. Additional exploratory analyses of the data will be conducted as deemed appropriate.

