## 5. A Priori Statistical Methods

### 5.1. General Considerations

Pharmacokinetic analyses will be conducted on the full analysis set (not including placebo). This set includes all data from all subjects receiving at least one dose of the investigational product.

Safety analyses will be conducted for all enrolled subjects who took study medication, whether or not they completed all protocol requirements.

Additional exploratory analyses of the data will be conducted as deemed appropriate. As this is a Phase 1 study and there will be no formal statistical hypothesis testing, any changes to the planned analysis will not necessitate a protocol amendment and will be detailed in the study report. Summary statistics, data tabulations, and data graphs by ethnicity (Japanese and non-Japanese, and combined) will be provided as appropriate.

Safety reporting will be conducted by Covance; with the exception of QTcF statistical analyses which will be conducted by Eli Lilly. All drug effects, PK, PD, imaging, cognition and exploratory reporting and analyses will be conducted by Eli Lilly.

Where two cohorts are given the same dose and formulation the patients will be pooled together and reported under the same dose levels. Placebo will be pooled across all cohorts.

In recognition that there are now only two dose cohorts in this study, any statistical models detailed in the analysis plan may still be carried out in order to estimate parameters, in particular where changes from baseline are being considered. Without recourse to statistical models, only those patients with both baseline and at least one post-baseline measurement can be included in any summary. Estimates from statistical models may provide additional information, if interpreted appropriately.

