## 5.7. Exploratory Pharmacodynamic Analyses

### 5.7.1. Pharmacodynamic Parameter Estimation

The concentration of plasma tau, and the concentration of CSF biomarkers, including tau, p-tau, A $\beta$ 1-42 and neurogranin, will be determined. Since protocol approval an additional parameter will be added to the assay; neurofilament light chain in CSF, this measure will be collected and treated as per the other parameters. Plasma and CSF biomarker data will be summarised statistically and/or illustrated graphically by time and dose. The mean change in concentration of the plasma and CSF biomarkers from predose will be evaluated.

No formal statistical analyses of these exploratory CSF/plasma biomarkers are planned.

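### The plasma and CSF biomarker objective is answered only by mean change from predose within each group; no baseline-adjusted LY3303560-versus-placebo estimate or interval is specified

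*Protocol*

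**What the plan says.** Table LMDD.1 (Protocol Section 4) sets the exploratory objective: "To evaluate the effects of multiple doses of LY3303560 on plasma and CSF biomarkers". The endpoints are plasma tau and CSF tau, p-tau, Aβ1-42 and neurogranin; SAP 5.7.1 adds CSF neurofilament light chain.

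For the analysis, Protocol 10.3.4.1 has two commitments: "Plasma and CSF biomarker data will be summarised statistically and/or illustrated graphically by time and dose", and "The mean change in concentration of the plasma and CSF biomarkers from predose will be evaluated". SAP 5.7.1 repeats both and adds "No formal statistical analyses of these exploratory CSF/plasma biomarkers are planned". Neither section names a scale (difference, percentage, ratio or log), a baseline adjustment, a difference from placebo or an interval.

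Three other places bear on this:

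- Protocol 10.3: "Patients receiving placebo will be pooled into 1 group". Placebo is therefore reported as a group of its own.
- SAP 5.1: "any statistical models detailed in the analysis plan may still be carried out in order to estimate parameters", in particular where changes from baseline are of interest. This covers only models that the plan sets out, and none is set out for the fluid biomarkers.
- SAP 5.6.1: SUVr, also exploratory and expressly not for hypothesis testing, gets a baseline-adjusted ANCOVA with a stated comparison against placebo.

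**The concern.** A pre-to-post change within a dose group is not a drug effect. It mixes the drug with disease progression, regression to the mean, assay drift and changes in the conditions that Protocol 9.4.8 lists as associated with plasma tau. Protocol 5.4 says that placebo is there so that PD data can be assessed without bias. A table of group means lets a reader compare dose with placebo by eye, but gives neither the estimated difference nor its uncertainty.

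Precision matters at this size. If a biomarker responds in proportion to its level, patients with high predose values dominate the mean change, and the spread of predose values enters its error. The CSF values cost each patient lumbar punctures, so it is worth drawing what they can give. At stake is a readable, reasonably precise estimate. No test would be passed or failed.

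**Working it through.** **Inputs from the documents.** "Each cohort will consist of 8 patients randomised (6 LY3303560: 2 placebo", in two cohorts, so 6 per dose and 2 + 2 = 4 pooled placebo. Protocol 10.1: "A total of 24 patients may be enrolled to ensure 16 complete the study"; 2 × 12 = 24 and 2 × 8 = 16 agree. The documents give no SD, effect size, alpha or power for any biomarker, so there is no planned figure to reproduce.

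**Assumptions.** True fall 25%; between-patient CV 20, 40 or 60%; within-patient CV (biology plus assay) 10 or 20%; all 16 patients have both samples.

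**Why the baseline spread matters.** Scale the mean predose level to 1. Let c be the between-patient CV, w the within-patient CV and m the ratio post/pre. With proportional effect and error, the variance of raw change in a treated arm is

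(1 + c²)·w²·(1 + m²) + (1 − m)²·c².

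With m = 0.75 and w = 0.10:

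- c = 0.2: 1.04 × 0.01 × 1.5625 + 0.0625 × 0.04 = 0.01625 + 0.0025 = 0.01875, SD 0.137.
- c = 0.6: 1.36 × 0.01 × 1.5625 + 0.0625 × 0.36 = 0.02125 + 0.0225 = 0.04375, SD 0.209.

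The log ratio has SD of about w√2 = 0.141 in both cases.

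**Simulation.** Each figure is the percentage of simulated trials in which the 90% interval for one dose against placebo excludes no effect. Residual degrees of freedom are 16 − 3 = 13 for unadjusted change and 16 − 4 = 12 for ANCOVA.

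*Effect and error both proportional, both doses lowering the biomarker by 25%:*

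| Within CV | Between CV | Raw change | Raw ANCOVA | Log ANCOVA |
|---|---|---|---|---|
| 10% | 20% | 84 | 92 | 92 |
| 10% | 40% | 76 | 88 | 90 |
| 10% | 60% | 64 | 83 | 89 |
| 20% | 20% | 40 | 54 | 51 |
| 20% | 40% | 36 | 48 | 46 |
| 20% | 60% | 33 | 42 | 44 |

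Raw ANCOVA gains 92 − 84 = 8 up to 83 − 64 = 19 points over raw change. Log ANCOVA differs from raw ANCOVA by 51 − 54 = −3 to 89 − 83 = +6 points. Most of the gain is therefore from adjustment, not from the log scale. With no true effect, raw change and log ANCOVA exclude it in about 9–11% of trials, near the nominal 10%.

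*Only the compared dose works:* raw change against log ANCOVA runs from about 83 vs 92 to 70 vs 88 at within-patient CV 10%, and from 37 vs 52 to 32 vs 44 at 20%. Raw ANCOVA gains less here, up to about 8 points over raw change, because one common slope fits the arms less well.

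*Proportional effect, additive error (both doses work):* raw change against log ANCOVA, at between-patient CV 20, 40 and 60%, is 81 vs 81, 74 vs 68 and 64 vs 56 with error SD 10% of the mean, and 36 vs 35, 33 vs 27 and 31 vs 22 with 20%. At CV 60% and error 10%, raw ANCOVA gives 78.

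*Additive effect and additive error, 10%:* raw change 82–84 against log ANCOVA 56–76. Raw ANCOVA loses at most about 3 points to raw change.

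**The case against.** The plan is descriptive by choice: no formal biomarker analysis, no hypothesis tests, about 16 completers. The share of intervals that exclude no effect measures performance against a decision rule that the study does not have. The wording on statistical summaries already permits geometric means or ratios, additional exploratory analyses are allowed, and optional PK/PD modelling (Protocol 10.3.5, SAP 5.7.3) may relate biomarkers to exposure. Protocol 3.3 looks for a PD effect primarily through flortaucipir, which has its model. Plasma tau is measured only if a suitable assay exists (Protocol 9.6).

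Much of this stands, and it keeps the priority low. It does not remove the gap. SUVr has the same exploratory, no-test status and still gets an adjusted placebo comparison, and an optional analysis is not a commitment. Cognition is a weaker precedent, since its MMRM is itself optional.

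A reader might infer more than the documents support:

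- *That placebo is left out.* It is pooled and shown; only the computed difference and its interval are missing.
- *That the plan commits to an arithmetic mean of raw differences.* That is the plain reading of mean change in concentration, but neither document says arithmetic or raw.
- *That log ratios are clearly better once effects are proportional.* The error must be proportional too. Without baseline adjustment, between-patient spread must also be substantial: with unadjusted log ratios at 6 versus 4 and two-sided 0.05, the median gain over 18 settings was about 1 point at between-patient CV 20%, against 16 at 60%. With additive error the log scale ties or loses. The documents do not say which kind of error applies.

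**Conclusion.** The point holds as a missing estimate. Protocol 10.3.4.1 and SAP 5.7.1 provide no baseline-adjusted LY3303560-versus-placebo estimate or interval for an objective that asks about drug effects, while SAP 5.6.1 does so for SUVr.

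Under the assumed CVs, raw-scale adjustment is the robust gain: from a loss of about 3 points at worst to a gain of about 8 where one dose works, and 8 to 19 where both do and error is proportional. The log scale is a trade-off. Its advantage over unadjusted change is about 9 to 18 points in the one-dose settings with within-patient CV 10% (92 − 83, 88 − 70), and it disappears or reverses with additive error. All sizes rest on assumed CVs, a 25% fall and complete pairs. Severity is low: the endpoints are exploratory and no decision in the documents depends on them.

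**What to change.** In SAP 5.7.1, with a matching line in Protocol 10.3.4.1, add for each plasma and CSF biomarker:

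1. An ANCOVA of the post-dose value on treatment (70 mg, 210 mg, pooled placebo) and predose value, giving each dose minus placebo with a 90% interval, labelled as estimation and not a test. Name the post-dose sample: CSF is taken at Visit 13, 19 or 20, or at early discontinuation, and plasma tau at many visits.
2. The geometric mean ratio to predose by dose and time, and the same model with log post-dose on treatment and log predose, giving an LY3303560/placebo ratio.
3. A statement of which scale leads, fixed before unblinding from assay precision or blinded predose data, with the other reported as supporting. Because Protocol 10.3.6 has the sponsor's study team unblinded for dose-escalation reviews and regularly reviewing PD data, post-dose values seen in those reviews should not inform the choice.
4. The mean-change summary, kept as planned.

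The cost is SAP wording, one extra table per biomarker and one or two residual degrees of freedom. Going from 13 to 12 moves the 90% t multiplier from 1.771 to 1.782, a factor of 1.782/1.771 = 1.006. No new samples or visits are needed.

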10.3.4.2. Cognition Analyses

ADAS-Cog14, NTB, MMSE, dCDT, and ADCS-MCI-ADL24 will all be summarised and may be analysed using an MMRM with preinfusion cognitive measures as a baseline covariate and fixed effects of dose and study visit. All cognition analyses are exploratory and underpowered to detect a clinically meaningful effect.

Correlations between cognition endpoints and flortaucipir F 18 SUV_r may be explored.

10.3.4.3. Evaluation of Immunogenicity

The frequency of antibody formation to LY3303560 will be determined. If a neutralisation assay is performed, the frequency of neutralising antibodies will be determined. The relationship between the presence (or absence) of antibodies and clinical parameters (AEs, efficacy measures, and so on) will be assessed. Likewise, the relationship between the presence of antibodies and the PK parameters and PD response to LY3303560 will be assessed.

10.3.5. Exploratory Pharmacokinetic/Pharmacodynamic Analyses

A model-based approach may be implemented using NONMEM or other appropriate software to estimate PK/PD parameters. Exploratory analyses may be conducted to characterise the relationship between changes in cognition endpoints, plasma and/or CSF biomarkers, and exposure of LY3303560.

